## 6.4. STATISTICAL TESTS

Unless otherwise specified:

- The default summary statistics for quantitative variables will be as follows:
  - o Number of participants in each category (n).
  - o Mean.
  - o Standard deviation (SD).
  - o Median.
  - o Minimum.
  - o Maximum.
- The default summary statistics for qualitative variables will be as follows:
  - o Number of participants in each category (n).
  - o Percentage of participants in each category (%), presented relative to either one of the following:
    - Total number of participants in the relevant analysis set.
    - Total number of participants in the relevant analysis set, with assessments available (observed cases).
- In the event of missing assessments, a 'Missing' category showing the number of participants with missing assessments at each level of summarization will be presented.
- Methods for determining confidence intervals (CIs) will be specified in each relevant section.

## 6.5. COMMON CALCULATIONS

The following common calculations are defined:

- $\text{Change from Baseline} = (\text{Result at relevant post-baseline time point} - \text{Result at Baseline})$ .
- **Most recent vaccination:**
  - o Calculate the difference in the start date of the assessment/event and all available study vaccination dates:
    - Days since dose x: (AE start date – study vaccination dose x date [where x = 1, 2 {not applicable for BCG}])
  - o For the previous calculation, only consider those doses where the days since dose x is  $\geq 0$  (therefore excluding the doses occurring after the relevant assessment/event) and determine the dose (1, 2 [not applicable for BCG]) for which the days since dose x (as calculated in the previous step) is a minimum.
  - o Assign the dose selected in the previous step as the most recent vaccination as the specific dose determined in the previous calculation.
- **Change from pre-vaccination:**
  - o Result at Study Day x – results at relevant pre-vaccination time point.
  - o If a result/value is missing, change from pre-vaccination result will be presented as missing in the listing. That is, no imputation for a missing change will be performed.

---

Document: Aeras\_C-040-404\_SAP\_V2\_0  
Author: [name]

Version Number: 2.0  
Version Date: 29SEP2017

Template No: CS\_TP\_BS016 – Revision 3  
Effective Date: 01May2012

Reference: CS\_WI\_BS005

- Shift in toxicity grade from pre-vaccination:
  - o Toxicity grade at Study Day x – toxicity grade at relevant pre-vaccination time point.
  - o If a toxicity grade is missing, shift in toxicity grade from pre-vaccination will be presented as missing in the listing. That is, no imputation for a missing shift will be performed.
  - o If no toxicity grade is assigned to a specific visit the grade will be regarded as grade 0 for calculation purposes.

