## 16.3. LABORATORY EVALUATIONS

The following tables are planned for presentation (based on the Safety analysis set for the Safety and Immunogenicity Cohort):

- Quantitative laboratory results and change from Baseline:
  - o Presented by means of default summary statistics for quantitative variables.
  - o Change from Baseline will be presented as well.
- Shift in laboratory grades from Baseline:
  - o Shift will be presented in terms of the number of participants with an increased toxicity grade from the Baseline result (refer to APPENDIX 7: Toxicity Grading Criteria):
    - 0 grades (no change in grade compared to Baseline or grade decreased).
    - 1 grade.
    - 2 grades.
    - 3 grades.
    - 4 grades (only applicable to certain tests).
  - o N1 is defined as the total number of participants with an assessment available at both Baseline and post-baseline time points.
  - o Due to the fact that the toxicity grading for Urine Erythrocytes is “Normal”, “Grade 1” or “Grade 2/3/4”, it is not possible to determine if there was an increase. Therefore Urine Erythrocytes will not be included in this table. The toxicity grading will be displayed in the listing.

The following listings are planned for presentation (based on the Randomized analysis set):

- Quantitative laboratory results.
- Qualitative laboratory results.
- Laboratory reference ranges by system and test (no analysis set applicable to this listing).

---

Document: Aeras\_C-040-404\_SAP\_V2\_0

Author: [name]

Version Number:

2.0

Version Date:

29SEP2017

Template No: CS\_TP\_BS016 – Revision 3

Reference: CS\_WI\_BS005

Effective Date: 01May2012

Copyright © 2012 Quintiles Transnational Corp. All rights reserved.

The contents of this document are confidential and proprietary to Quintiles Transnational Corp. Unauthorized use, disclosure or reproduction is strictly prohibited.

Refer to APPENDIX 5: Laboratory Assessments for a list of laboratory assessments.

The following laboratory variables, as presented in the planned TLF shells, will be collected during the study on the Hematology (HEMA), Chemistry (CHEM), Urinalysis (URIN), Pregnancy Test (PREG) and HIV Tests (HIVT) eCRFs:

- Date of sample collection.
- Time of sample collection (only applicable to pregnancy test results).
- Test.
- Reported results and unit.

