### 16.3.1. TOXICITY GRADING CRITERIA

The toxicity grades will be assigned based on the protocol-specific criteria specified in APPENDIX 7: Toxicity Grading Criteria. For some assessments grade 3 or 4 cannot be assigned programmatically, but rather are based on clinical judgment, therefore they are not assigned for the purpose of analysis.

Refer to APPENDIX 5: Laboratory Assessments for a list of tests for which toxicity grades will be programmatically assigned.

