### DECIMAL PRECISION

All values will be rounded using the SAS® function ROUND, as the last step prior to presentation. All computed percentages (%) will be presented using one decimal place. If the original data has N decimal places (as derived

---

Document: Aeras\_C-040-404\_SAP\_V2\_0  
Author: [name]

Version Number: 2.0  
Version Date: 29SEP2017

Template No: CS\_TP\_BS016 – Revision 3  
Effective Date: 01May2012

Reference: CS\_WI\_BS005

from the raw data), then the summary statistics for quantitative data are to contain the following number of decimal places (with a maximum of 3 places):

- Minimum and maximum: N.
- Mean and median: (N+1).
- Standard deviation: (N+2).

All p-values will be presented with 4 decimal places, if less than 0.0001 (after rounding to 4 decimal places) the p-value will be displayed as <0.0001. Odds ratios will be presented to 3 decimals and CIs will be presented to 2 decimals.

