## APPENDIX 5. LABORATORY ASSESSMENTS

System Test	Reported Unit	Conversion Factor	SI Unit	Toxicity Abnormality*
Hematology				
Basophils	10  /L	1	10  /L	-
Eosinophils	10  /L	1	10  /L	-
Hematocrit	Fraction of one	1	Fraction of %	-
	L/L	1	Fraction of %	-
Hemoglobin	g/dL	10	g/L	Hemoglobin -decreased
Lymphocytes	10  /L	1	10  /L	-
Monocytes	10  /L	1	10  /L	-
Neutrophils	10  /L	1	10  /L	-
Platelet count	10  /L	1	10  /L	Platelets - decreased
White blood cell (WBC) count	10  /L	1	10  /L	WBC - decreased
				WBC - increased
Chemistry				
Alkaline phosphatase	U/L	1	U/L	Alkaline phosphatase - increased
ALT	U/L	1	U/L	ALT (SGPT) - increased
AST	U/L	1	U/L	AST (SGOT) - increased
Blood urea nitrogen	mg/dL	0.357	mmol/L	BUN - increased
	mmol/L	1	mmol/L	
Creatinine	μmol/L	1	μmol/L	Creatinine - increased
Total bilirubin	μmol/L	1	μmol/L	Total bilirubin - increased
Urinalysis				
Blood	No standardization performed for the urinalysis laboratory assessments			-
Glucose				-
Protein				Proteinuria, random collection
Leucocytes				-
Erythrocytes				Hematuria
Epithelial cells				-

\*Refer to APPENDIX 7: Toxicity Grading Criteria.

Document: Aeras\_C-040-404\_SAP\_V2\_0

Author: [name]

Version Number:

2.0

Version Date:

29SEP2017

Template No: CS\_TP\_BS016 – Revision 3

Reference: CS\_WI\_BS005

Effective Date: 01May2012

Copyright © 2012 Quintiles Transnational Corp. All rights reserved.

The contents of this document are confidential and proprietary to Quintiles Transnational Corp. Unauthorized use, disclosure or reproduction is strictly prohibited.

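### Gaps between the printed ALT, AST, ALP and bilirubin grade bands, combined with the SAP's Grade 0 rule, let a clearly raised value count as no shift in one laboratory table (low impact)

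*SAP*

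**What the plan says.** SAP Appendix 7 (Laboratory: Chemistry) prints the following bands, in multiples of ULN. The toxicity table in protocol Appendix B has the same ones.

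| Test | Grade 1 | Grade 2 | Grade 3 | Grade 4 |
|---|---|---|---|---|
| ALT, AST, ALP | 1.25-2.5 | 2.6-5.0 | 5.1-10.0 | >10.0 |
| Total bilirubin | 1.1-1.5 | 1.6-2.5 | 2.6-5.0 | >5.0 |

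SAP 16.3.1 has these grades derived by program: "Refer to APPENDIX 5: Laboratory Assessments for a list of tests for which toxicity grades will be programmatically assigned". ALT is on that list as "ALT (SGPT) - increased", and AST, ALP and bilirubin are listed too. The only rounding instruction is under Decimal Precision in SAP Appendix 1: "All values will be rounded using the SAS® function ROUND, as the last step prior to presentation".

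SAP 6.5 gives two adjacent rules for shifts in grade. The first is "If a toxicity grade is missing, shift in toxicity grade from pre-vaccination will be presented as missing in the listing". The second is "If no toxicity grade is assigned to a specific visit the grade will be regarded as grade 0 for calculation purposes".

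The output affected is the shift table in SAP 16.3, which is "based on the Safety analysis set for the Safety and Immunogenicity Cohort". Its lowest row is "0 grades (no change in grade compared to Baseline or grade decreased").

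**The concern.** A program that applies the printed limits to an unrounded multiple of ULN finds no band for a value such as 2.55 or 5.05. The second rule in SAP 6.5 then turns that absence into Grade 0. Grade 0 is sensible for a result below the Grade 1 limit, which is presumably what the sentence was written for. As worded, it also catches measured results that lie above Grade 1 or above Grade 2 but fall between two printed edges. A participant whose ALT had risen to more than five times ULN could then be tabulated with those who had no change.

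**Working it through.** The plan gives no figure of its own here, so the check is to apply its rules as printed.

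**Step 1: grade the multiple.** Let r = result / ULN, unrounded. Under the ALT bands:

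| r | 2.50 | 2.55 | 2.60 | 5.00 | 5.05 | 5.10 |
|---|---|---|---|---|---|---|
| Grade | 1 | none | 2 | 2 | none | 3 |

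Bilirubin at 1.55 and 2.55 times ULN likewise has no grade.

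**Step 2: apply SAP 6.5.** No grade becomes Grade 0. Exclusion criterion 3 in protocol 3.2.4 rules out ALT above 1.25 times ULN, so the baseline grade is 0, or 1 only at exactly 1.25. The shift is therefore 0 - 0 = 0, or 0 - 1 = -1. Both belong in the lowest row of the shift table.

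**Step 3: compare with rules that leave no gap.**
- Rounding r half-up to one decimal: 2.55 becomes 2.6 (Grade 2) and 5.05 becomes 5.1 (Grade 3).
- Running each lower band up to the start of the next: 2.55 is Grade 1 and 5.05 is Grade 2.

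Against either rule, the tabulated grade is too low by 1 to 2 grades at 2.55 and by 2 to 3 grades at 5.05.

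**Step 4: are such results reachable?** The documents give no ULN, so I assume a range. The ungraded results lie strictly between 2.5 x ULN and 2.6 x ULN, and between 5.0 x ULN and 5.1 x ULN.

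| Assumed ULN (U/L) | First gap | Whole-number ALT | Second gap | Whole-number ALT |
|---|---|---|---|---|
| 25 | 62.5 to 65 | 63-64 | 125 to 127.5 | 126-127 |
| 40 | 100 to 104 | 101-103 | 200 to 204 | 201-203 |
| 60 | 150 to 156 | 151-155 | 300 to 306 | 301-305 |

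Ordinary laboratory values can therefore land in a gap, although each gap is only 0.1 x ULN wide.

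**Step 5: how many participants?** The cohort is planned at 90. Post-vaccination chemistry is taken at Day 7 in all three arms and again at Day 63 in the two H4:IC31/placebo arms (60 participants). One expected case at Day 7 would require 1/90 = 1.1% of participants to fall inside these narrow windows. The documents give no distribution of post-vaccination values. For healthy adolescents screened at 1.25 times ULN, I take the expected number to be well below one per visit.

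**Side check: creatinine.** The printed pairs are 1.5/121, 1.7/145, 1.8/146, 2.0/170, 2.1/171 and 2.5/208 (mg/dL / umol/L). Allowing for rounding of both figures, the pair 2.0/170 needs a conversion factor of at least 169.5/2.05 = 82.7, and the pair 2.1/171 needs at most 171.5/2.05 = 83.7. The columns therefore agree only for a factor between 82.7 and 83.7. With an assumed 88.4, which is not in the documents, 1.5, 1.8 and 2.1 mg/dL are 132.6, 159.1 and 185.6 umol/L, against the printed 121, 146 and 171.

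**The case against.** The best defence is that nobody would program it this way. The inner band edges are printed to one decimal, which suggests that the multiple is meant to be rounded first. The instruction to round "as the last step prior to presentation" sits among output conventions and does not forbid an earlier rounding for grading. The first sentence of SAP 6.5 might also be read as covering these values, making the shift missing. In addition, the Grade 0 sentence stands under shift from pre-vaccination, whereas the laboratory table speaks of Baseline.

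Part of this stands. The Grade 0 result follows from the literal text; the SAP does not set out to treat these values as normal. But the SAP does not state rounding before grading, and the Grade 1 limit of 1.25 does not fit a one-decimal convention. The missing-grade sentence concerns the listing and does not address a measured value that fits no band. SAP 6.2 treats the Baseline assessment as pre-vaccination, and no separate rule is given for the laboratory table. The choice also matters, because Step 3 shows that two reasonable programmers would give the same result different grades.

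A reader might go further and infer that the plan conceals liver toxicity in its primary safety analysis. The documents do not support that. The primary safety variable in protocol 7.5.1 is solicited and unsolicited adverse events. The result itself remains in the quantitative summary, the change from Baseline and the listings of SAP 16.3. It may also be reported as an adverse event under protocol 3.6.3.2, although that trigger is a rise in grade on a table with the same gaps.

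A reader might also infer that creatinine will be misgraded. It will not be by this route: SAP Appendix 5 takes creatinine in umol/L only, and those bands are contiguous for whole numbers.

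**Conclusion.** The point holds on the text and is minor. Taken together, SAP 6.5 and Appendix 7 put a measured value between two printed hepatic bands into the row for no change or decrease. The effect is limited to one shift table in a planned cohort of 90. If a case occurred, the tabulated grade would be too low by 1 to 3 grades. No efficacy result is touched.

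The conclusion rests on applying the printed limits without prior rounding. The U/L figures rest on the assumed ULN range of 25 to 60, and the expected count is a judgement about healthy adolescents, not a figure from the documents. The creatinine mismatch is a side note that depends on an assumed factor and changes no programmed grade.

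**What to change.** Make two edits before the grading is programmed.

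1. State one rule that gives every measured value a grade: either contiguous bands, or a stated rounding of the ULN multiple before grading. The sponsor should choose it and keep it consistent with protocol Appendix B, because investigators grade from that table and the Grade 3 and 4 rules in protocol section 6 refer to toxicity grades. The choice also affects other edges. For example, rounding to one decimal would bring a bilirubin of 1.05 times ULN into Grade 1.
2. In SAP 6.5, limit Grade 0 to non-missing results that do not reach the Grade 1 threshold, and leave the grade missing when the result is missing.

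In the same pass, reconcile the mg/dL and umol/L creatinine columns between SAP Appendix 7 and protocol Appendix B. I do not say which column is right.

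The cost is a few lines of specification, with no new data.

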## 6.6. SOFTWARE VERSION

All analyses will be conducted using SAS® Version 9.4.

## 7. STATISTICAL CONSIDERATIONS

### 7.1. ADJUSTMENTS FOR COVARIATES AND FACTORS TO BE INCLUDED IN ANALYSES

Not applicable.

### 7.2. MULTICENTER STUDIES

This study is being conducted by multiple Investigators at multiple schools/regions in South Africa. No adjustment for school/region effect will be made. Generally, all schools/regions will be pooled by cohort and treatment group for analysis purposes.

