### 3.3 Study Randomization

Subjects will be randomized to the study based on a randomly-generated sequence of subject identification numbers (randomization schedule) managed by a validated IVRS/IWRS. The randomization schedule will be prepared by a statistician who will not be involved in the analysis of the study in order to maintain the blind of the study team. The day of randomization for each subject will be Study Day 0. Randomization will be in blocks for each school or community, as

the epidemiology of TB transmission may vary from one school or community to another. Randomization will also be blocked such that 30 subjects from each vaccine group will be enrolled in the Safety & Immunogenicity Cohort. Enrollment for the Safety & Immunogenicity Cohort will be from a subset of schools or communities selected to be representative of the study population as a whole in terms of socio-economic status and TB risk. Subjects who discontinue participation will not be replaced.

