#### 14.1.2. ANALYSIS OF PRIMARY EFFICACY ENDPOINT

The following tables will be presented for the Modified Intent-to-treat analysis set:

- QFT-GIT results at each visit:
  - o Number and percentage (%) of participants in each category per visit:
    - Negative.
    - Positive.
    - Missing.
  - o Percentage (%) of participants will be calculated relative to the total number of participants in the Modified Intent-to-treat analysis set who have QFT-GIT assessments available per treatment group per visit.

---

Document: Aeras\_C-040-404\_SAP\_V2\_0

Author: [name]

Version Number:

2.0

Version Date:

29SEP2017

Template No: CS\_TP\_BS016 – Revision 3

Reference: CS\_WI\_BS005

Effective Date: 01May2012

Copyright © 2012 Quintiles Transnational Corp. All rights reserved.

The contents of this document are confidential and proprietary to Quintiles Transnational Corp. Unauthorized use, disclosure or reproduction is strictly prohibited.

- Compliance to QFT-GIT testing:
  - o Number and percentage (%) of participants in each compliance category per visit:
    - Yes.
    - No.
    - Missing.
  - o Percentage (%) of participants will be calculated relative to the total number of participants in the Modified Intent-to-treat analysis set expected to have a QFT-GIT assessment available per treatment group per visit (N1).
- QFT-GIT conversion rates, primary endpoint (therefore endpoints occurring after Day 84):
  - o Number and percentage (%) of participants in each conversion status category:
    - Yes.
    - No.
    - Missing.
  - o Hazard ratio (H4:IC31/comparator) presented:
    - Point estimates (based on the Cox regression model).
    - P-values for the comparison of the estimated hazard ratios of QFT-GIT conversion based on a one-sided log-rank test.
      - H4:IC31 versus Placebo.
      - BCG versus Placebo.
      - H4:IC31 versus BCG (at the request of the sponsor's partner).
  - o Vaccine efficacy presented:
    - Point estimate (based on the hazard ratio estimates).
    - 80% two-sided CI based on the hazard ratio estimate from the Cox regression model.
  - o This table will be repeated for the Per Protocol, Adjusted Modified Intent-to-treat (First Recall Positive Omit) analysis sets. This table will also be repeated for the adjudication approach (refer to Section 3.3: Changes to Analysis from Protocol).

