  - o As a sensitivity analysis the content of this table will be repeated in a separate table using interval censoring for the MITT analysis set.
- First QFT-GIT conversion by visit:
  - o Number and percentage (%) of participants with first QFT-GIT conversion at each of the scheduled visits.
  - o Number of participants at risk for first conversion at each scheduled visit.
  - o At risk defined as participants with:
    - A negative QFT-GIT result at the preceding visit without a previous positive QFT-GIT result.
    - A QFT-GIT result available at the relevant visit.
  - o This table will be repeated for the Per Protocol analysis set.
- Follow-up time until first QFT-GIT conversion:
  - o Number of participants contributing to the total follow-up time (at risk).
  - o Cumulative number of participants:
    - Censored (not due to a primary endpoint at the time of the last available non-positive QFT-GIT result).
    - With an event (primary endpoint).
  - o The total follow-up time (person-months), as measured from Randomization (1 month = 4 weeks).
  - o The Kaplan-Meier event rate presented at each relevant post-Day 84 visit.
  - o This table will be repeated for the Per Protocol analysis set.

Document: Aeras\_C-040-404\_SAP\_V2\_0

Author: [name]

Version Number:

2.0

Version Date:

29SEP2017

Template No: CS\_TP\_BS016 – Revision 3

Reference: CS\_WI\_BS005

Effective Date: 01May2012

Copyright © 2012 Quintiles Transnational Corp. All rights reserved.

The contents of this document are confidential and proprietary to Quintiles Transnational Corp. Unauthorized use, disclosure or reproduction is strictly prohibited.

- Primary endpoints by school/region:
  - o Number and percentage (%) of participants who experienced a primary endpoint in each school/region.
- Primary endpoints by site and sex:
  - o Number and percentage (%) of participants who experienced a primary endpoint in each site/sex.

The following table will be presented for the Randomized analysis set:

- QFT-GIT conversion rates including all post-Day 0 conversions:
  - o Number and percentage (%) of participants in each conversion status category:
    - Yes.
    - No.
    - Missing.
  - o Two groups of conversion time points included:
    - Any QFT-GIT conversion (early [Day 84] or post-Day 84) (at risk participants include all participants).
    - Early (Day 84) conversion (at risk participants include all participants).
  - o Hazard ratio (H4:IC31/comparator) presented:

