  - o For the sensitivity analysis the following SAS code will be implemented:

```
PROC LIFETEST DATA = <> METHOD=lt INTERVALS=(0 to 2 by 0.5)
PLOTS=(s) ;
TIME Years*Censored(1) ;
FREQ count;
RUN;
```

- Vaccine efficacy is derived as:
  - o  $VE = 1 - \text{Hazard Rate Ratio (Vaccine/comparator)}$
  - o The hazard ratio is estimated based on the following Cox regression model:

```
PROC PHREG DATA = <>;
MODEL Time to Event (Months) * Censor (1) = Treatment Group;
RUN;
```

- Censor = 1 represents censored participant.
    - Censor = 0 represents participant who experienced an event.
    - Months represent the available follow-up time (months) per participant since randomization.
  - o The 80% CI is based on the two-sided hazard ratio confidence interval and will be derived as:
    - $VE_{\text{lower limit}} = 1 - \text{Hazard ratio}_{\text{upper limit}}$
    - $VE_{\text{upper limit}} = 1 - \text{Hazard ratio}_{\text{lower limit}}$
  - o The 95% CI is based on the two-sided hazard ratio confidence interval.

- For the sensitivity analysis, interval censoring will be used based on the following code:

```
PROC ICPHREG DATA = <>;
MODEL (left, right) = Treatment Group /b=pch(NINTERVAL=X);
RUN;
```

- Left represents left censoring value in months.
  - Right represents right censoring value in months.
  - Left and right censoring values are dependent on where the event is identified:

Visit at Which Primary Event Identified	Left Censoring Value	Right Censoring Value
M6	3	6
M12	6	12
M18	12	18
M24	18	24

Document: Aeras\_C-040-404\_SAP\_V2\_0

Author: [name]

Version Number:

2.0

Version Date:

29SEP2017

Template No: CS\_TP\_BS016 – Revision 3

Reference: CS\_WI\_BS005

Effective Date: 01May2012

Copyright © 2012 Quintiles Transnational Corp. All rights reserved.

The contents of this document are confidential and proprietary to Quintiles Transnational Corp. Unauthorized use, disclosure or reproduction is strictly prohibited.

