### 14.2.2. ANALYSIS OF SECONDARY EFFICACY ENDPOINT

The following table will be presented for the Modified Intent-to-treat analysis set:

- QFT-GIT 6-month sustained conversion rates:
  - o Number and percentage (%) of participants in each conversion status category:
    - Yes.
    - No.
    - Missing.
  - o Hazard ratio (H4:IC31/comparator) presented:
    - Point estimates (based on the Cox regression model).
    - P-values for the comparison of the estimated hazard ratios of QFT-GIT 6-month sustained conversion based on a one-sided log-rank test.
      - H4:IC31 versus Placebo.
      - BCG versus Placebo.
      - H4:IC31 versus BCG (at the request of the sponsor's partner).
  - o Vaccine efficacy presented:
    - Point estimate (based on the hazard ratio estimate).
    - 80% two-sided CI based on the hazard ratio estimate from the Cox regression model.
  - o This table will be repeated for the alternative threshold value.
  - o These tables (based on the original threshold as well as the alternative threshold) will be repeated for the Per Protocol analysis set. This table (based on the original threshold) will also be repeated for the Adjusted Modified Intent-to-treat (First Recall Positive Omit) analysis set and the adjudication approach (refer to Section 3.3: Changes to Analysis from Protocol).
  - o As a sensitivity analysis both of these tables (original threshold and the alternative threshold outputs) will be repeated in separate tables using interval censoring for the MITT analysis set.

---

Document: Aeras\_C-040-404\_SAP\_V2\_0

Author: [name]

Version Number:

2.0

Version Date:

29SEP2017

Template No: CS\_TP\_BS016 – Revision 3

Reference: CS\_WI\_BS005

Effective Date: 01May2012

Copyright © 2012 Quintiles Transnational Corp. All rights reserved.

The contents of this document are confidential and proprietary to Quintiles Transnational Corp. Unauthorized use, disclosure or reproduction is strictly prohibited.

The following figures will be presented for the Modified Intent-to-treat analysis set:

- Time to 6-month sustained QuantiFERON conversion:
  - o Kaplan-Meier plots per treatment group for the following:
    - Time to first of three consecutive post-Day 84 QFT-GIT positive results.
  - o Time to sustained QFT-GIT conversion will be presented in months, measured from Day 84 (1 month = 4 weeks) to the date of the first of three consecutively positive QFT-GIT results.

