  - Vaccine efficacy is derived as:
    - o  $VE = 1 - Hazard\ Ratio\ (Vaccine/comparator)$
    - o The hazard ratio is estimated based on the following Cox regression model:

```
PROC PHREG DATA = <>;
    MODEL Time to Event (Months) * Censor (1) = Treatment_Group;
RUN;
```

- Censor = 1 represents censored participant.
      - Censor = 0 represents participant who experienced an event.
      - Months represent the available follow-up time (months) per participant since Day 84.
    - o The 80% CI is based on the two-sided hazard ratio confidence interval and will be derived as:
      - $VE_{lower\ limit} = 1 - Hazard\ ratio_{upper\ limit}$
      - $VE_{upper\ limit} = 1 - Hazard\ ratio_{lower\ limit}$
    - o The 95% CI is based on the two-sided hazard ratio confidence interval.

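### Randomisation is blocked by school or community, but the final analysis pools them without a stated reason; if conversion rates differ, the test is slightly conservative and a little power is lost

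*SAP*

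**What the plan says.** Protocol 3.3 states: "Randomization will be in blocks for each school or community". Its reason is that "the epidemiology of TB transmission may vary from one school or community to another".

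SAP 7.1 lists no covariates or factors for the analyses. SAP 7.2 says "No adjustment for school/region effect will be made" and pools schools and regions.

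The planned analyses follow that:
- Primary endpoint (SAP 14.1.2): "P-values for the comparison of the estimated hazard ratios of QFT-GIT conversion based on a one-sided log-rank test". The Cox model in 14.1.3 has treatment group as its only term.
- Secondary endpoint (SAP 14.2.2): "P-values for the comparison of the estimated hazard ratios of QFT-GIT 6-month sustained conversion based on a one-sided log-rank test". The model in 14.2.3 is "MODEL Time to Event (Months) * Censor (1) = Treatment_Group".

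School and region enter the efficacy outputs only descriptively, in a table giving "Number and percentage (%) of participants who experienced a primary endpoint in each school/region". SAP section 10 lists 11 named schools and 7 named regions, each list with an open category, and section 9 gives two site codes. The factor is therefore already in the database.

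Protocol 7.3 also names a log-rank test without strata, so the SAP and protocol agree with each other. The mismatch is between the randomisation and the analysis.

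**The concern.** The protocol treats school or community as potentially prognostic for the primary endpoint and balances the arms within it. When strata differ in risk, blocking removes the between-stratum part of the variation in the treatment comparison. A pooled log-rank test still counts that part in its variance. The test then becomes conservative, and the pooled hazard ratio moves slightly towards 1.

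What is at stake is efficiency: some power, and a small attenuation of the reported vaccine efficacy, for both vaccine comparisons on both endpoints. Validity is not at stake. SAP 7.4 argues its choice on multiplicity at length, whereas SAP 7.2 offers no argument for setting aside the factor used in randomisation.

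**Working it through.** **Inputs from the documents.** Protocol 7.6: one-sided alpha 0.10, power 80%, 50% reduction (HR 0.5), 10% conversion per year, 7% loss per year, 64 endpoints from 990 subjects, 6-monthly visits to 24 months. Allocation is 1:1:1, 330 per arm (Protocol 2.2).

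**The plan's own figure.** Schoenfeld events per pair = 4(1.2816 + 0.8416)² / (ln 0.5)² = 18.03 / 0.4805 = 37.5, so 38. If one vaccine has HR 0.5 and the other has no effect, a vaccine-placebo pair holds 1.5/2.5 of all events, so the total is 38 × 2.5/1.5 = 63.3, i.e. 64. Conversely, 64 × 0.6 = 38.4 events gives power Φ(√38.4/2 × 0.6931 − 1.2816) = Φ(0.866) = 0.807. The stated design reproduces and does not depend on stratification.

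**Tests compared.** At each visit the log-rank score is O − d·n₁/N, with variance d·n₀·n₁(N − d)/{N²(N − 1)}. The pooled test sums over visits. The stratified test computes both quantities within each stratum and sums over visits and strata. Both reject when Z is beyond 1.2816 in the vaccine's favour.

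**Simulation assumptions.** 40,000 replicates per setting; 330 per arm; testing at Days 168, 336, 504 and 672 in those negative at Day 84; stratum rates gamma-distributed with the stated CV and the overall mean held fixed. Strata: 2 sites (assumed 70/30), 11 unequal schools, or 20 unequal strata (11 schools plus other, 7 regions plus other). Monte Carlo SE is at most 0.0015 for size and 0.0025 for power; paired differences are more precise.

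**Final primary analysis** (about 92 pairwise events under the null when strata do not differ). Entries are for 2 sites / 11 schools / 20 strata.

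| | CV 0.5 | CV 1.0 |
|---|---|---|
| Size, pooled | 0.101 / 0.097 / 0.095 | 0.098 / 0.089 / 0.088 |
| Size, stratified | 0.103 / 0.100 / 0.098 | 0.104 / 0.101 / 0.100 |
| Power gain, efficacy 50% (points) | 0.1 / 0.1 / 0.3 | 0.5 / 0.8 / 0.9 |
| Power gain, efficacy 35% (points) | 0.2 / 0.6 / 0.5 | 1.1 / 2.3 / 2.5 |

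With 20 strata at CV 1.0, power goes from 0.922 to 0.931 at 50% efficacy and from 0.677 to 0.702 at 35%. At CV 0 to 0.25 the change is −0.1 to +0.1 points.

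**Secondary endpoint** (10% × (1 − 0.20) = 8% per year, using the reversion rate in Protocol 7.6; about 74 null events; 20 strata). At CV 0.5, size goes from 0.098 to 0.101 and power at 50% efficacy from 0.895 to 0.898. At CV 1.0, size goes from 0.090 to 0.100 and power from 0.876 to 0.886.

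**Downside at the 64-endpoint size** (about 35 pairwise events at 50% efficacy). Stratifying by 20 strata changes power by −0.6, −0.5, −0.1 and +0.7 points at CV 0, 0.25, 0.5 and 1.0. With 2 sites the change is 0.0 to +0.5.

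**Cross-check with log-normal stratum rates** (18 strata, 40,000 replicates). The SD of the pooled Z falls from 1.00 with no spread to 0.947 at an SD of log rate of 1.0. That implies a size of Φ(−1.2816/0.947) = Φ(−1.353) = 0.088, against 0.089 simulated. Power at HR 0.5, pooled to stratified, is 0.931 to 0.932 at SD 0.5 and 0.888 to 0.901 at SD 1.0. The pooled hazard ratio is 0.509 against 0.503 stratified at SD 0.5, and 0.525 against 0.501 at SD 1.0, i.e. efficacy 47.5% against 49.9%. At the 17% per year rate also cited in Protocol 7.6, the gain is 0.1 points at SD 0.5 and 0.9 at SD 1.0. With 40 strata and little or no spread, stratifying costs about 0.3 points.

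**The case against.** The SAP carries out the test that the protocol names and sized. SAP 7.2 addresses school/region openly and declines to adjust, so what is missing is a reason.

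The gains are small. At the design effect and CV 0.5 they are 0.1 to 0.3 points, on power well above 80%. With two sites at CV 0.5 the pooled test is not conservative at all (0.101), and the stratified test reads 0.103 to 0.104. The larger gains need a CV of 1.0, which for a gamma distribution means a 90th/10th percentile rate ratio of ln 0.1/ln 0.9, about 22, and the largest also need 35% efficacy. The protocol requires additional sites to have comparable TB epidemiology.

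At 64 endpoints, stratifying by 20 strata costs power unless the spread is large, and that analysis has already been done under a separate SAP. Changing the headline test after the Data Monitoring Committee has seen unblinded results also carries a credibility cost.

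All of this stands as a limit on size, and it is why the point is minor. It does not remove the point. Protocol 3.3 itself allows that schools differ, the final analysis has more events than the 64-endpoint one, and SAP 3.1 records that the blind was kept until study completion. A change made before unblinding, with the unstratified results beside it, is defensible.

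**Conclusion.** The concern holds, as a minor point of efficiency. If conversion rates vary between schools or regions, the pooled final test is slightly conservative (down to about 0.088 against 0.10) and gives up power: a few tenths of a point at moderate spread, about 1 point at large spread under the protocol's 50% effect, and up to 2.5 points at an assumed 35% effect. Type I error is not inflated, the stated 80% power is unaffected, and no protocol text is contradicted.

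The size rests on assumptions the documents cannot settle: the between-stratum spread, the number and sizes of strata, the site split, and arms closely balanced within strata. If the spread is small, nothing is gained. The point concerns the final analysis only.

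**What to change.** Before final unblinding, amend SAP 7.2, 14.1 and 14.2:

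1. For each pairwise comparison, stratify the final primary and secondary analyses by school/region: PROC LIFETEST with `STRATA school_region / GROUP=treatment`, and PROC PHREG with `STRATA school_region`. First confirm that the recorded school/region categories match the blocks used in randomisation.
2. Fix a sparse-stratum rule on blinded counts. For example, merge schools/regions with fewer than 45 mITT participants over the three arms into one stratum within their site; if that stratum is still under 45, add it to the smallest remaining stratum at the site. In the 20-stratum simulation this leaves 13 strata and keeps most of the gain at CV 1.0 (0.677 to 0.698 at 35% efficacy, 0.922 to 0.929 at 50%).
3. Report the unstratified log-rank and Cox results alongside, for comparison with the protocol's test and the completed primary analysis.
4. Say whether the interval-censored sensitivity model stays unstratified.

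Cohort need not be a further stratum: it holds 30 of 330 per arm, about 8 of 92 pairwise events.

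The cost is text in three SAP sections, one statement per program and one extra set of tables, with no new data. If strata do not differ, the power loss at the final event count is about 0.1 to 0.3 points, depending on the number of strata; at the 64-endpoint size it is up to 0.6. If the sponsor keeps the pooled test as the headline, it should at least prespecify the stratified analysis as a sensitivity analysis and state in 7.2 why the randomisation factor is left out.
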